Risks of Lorcaserin Administration

Lorcaserin is FDA approved for the treatment of obesity. According to the FDA briefing document on lorcaserin based on the clinical trials in patients with obesity, “the most common adverse events with an incidence in the lorcaserin group that clearly exceeded placebo were headache (16.8 vs. 10.1%), dizziness (8.5 vs. 3.8%), nausea (8.3 vs. 5.3%), fatigue (7.2 vs. 3.6%), and dry mouth (5.3 vs. 2.3%). These events were typically dose-related, mild or moderate in severity and transient. Furthermore, the excess over placebo occurred primarily within the first several days of treatment for headache and dizziness. Rates of discontinuation for adverse events were similar for lorcaserin 10 mg BID (8.6%), 10 mg QD (7.5%), and placebo (6.8%). Serious adverse events were as expected for the population, and similar in both character and frequency in the lorcaserin and placebo populations.” Because lorcaserin has the potential to impair cognitive function, patients should be cautioned about operating hazardous machinery, including automobiles, until they are reasonably certain that lorcaserin therapy does not affect them adversely. In preclinical studies abnormalities in thyroid function and liver tests have been seen in animals, but no changes in thyroid function or liver function have been noted in humans. In patients with diabetes, a drop in blood sugar has been seen. Weight loss may increase the risk of hypoglycemia in patients with type 2 diabetes mellitus treated with insulin and/or insulin secretagogues (e.g., sulfonylureas); hypoglycemia was observed in clinical trials with lorcaserin. Lorcaserin has not been studied in combination with insulin. In other populations, lorcaserin has been associated with a modest increase in blood pressure.

Other Potential Risks of Lorcaserin but not seen in Clinical Trials

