In a recent NIDA funded preclinical study (NIDA Study Report 1812-12132, Sep. 20, 2013), lorcaserin was administered to rodents in combination with cocaine without any significant toxicity. Final results of this study are summarized here and provided in detail in an attached document. In short, at human equivalent doses in rats (i.e., 5 mg/kg, equivalent to 20 mg/day in humans, based on systemic exposures), there were no additive/synergistic effects of PO lorcaserin on IV cocaine-induced mortality or convulsions. However, at 5-fold higher doses (i.e., 25 mg/kg in rats, equivalent to 100 mg/day in humans – substantially beyond what is proposed in this study), there are indications of increased sensitivity to cocaine-induced convulsions due to lorcaserin. The combination of lorcaserin and cocaine has not been studied in humans. We will guard against potential toxicity of cocaine combined with lorcaserin by dosing cocaine using an ascending dose approach, and we have specific stopping criteria in place to stop the cocaine dose escalation if warranted by excessive cardiovascular responses. If in spite of these precautions cocaine toxicity is observed (significant hypertension, tachycardia, symptoms of ischemia or evidence of arrhythmias) we have established treatment protocols in place and a code team will respond if needed. We have never required such assistance in the past. Moreover, additional blood samples will be drawn 4-6 hours on the days of escalating cocaine infusions to measure high-sensitivity troponin I (hsTnI) and N-terminal pro-brain natriuretic peptide (NT-pro-BNP). Although not routinely utilized in clinical practice, these markers will be stored for batch analysis upon completion of the study to detect the presence cardiac strain and/or stress to the myocardium related to cocaine in the absence of overt clinical disease (Gaggin and Januzzi, 2014; Gualandro et al., 2014). This data will be used as a potential biomarker of subclinical effects of cocaine on heart for future clinical trials. The total amount of blood for the entire study will not exceed 550ml in an 8 week period.

Potential Risks Not Due to Study Medication

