Update concomitant medications.

Administer cocaine for PK.

Measure lorcaserin PK.

Conduct clinical assessments (POMS, CGI-I).

Administer cocaine for Dosing session 4.

Administer IMT task

Administer placebo/lorcaserin in evening
Leave CRS unit.

Study Day 11

Arrive on CRS unit
Administer placebo/lorcaserin in morning
Collect urine for pregnancy test and urine drug screen.
Collect blood for clinical laboratory tests (serum chemistry and hematology).
Perform and record Breathalyzer and vital signs.
Perform a 12-Lead ECG and continuous cardiovascular monitoring.
Record brief substance craving scale, VAS and AE.
Administer COWS if opioid user.
Update concomitant medication.
Self -Administered cocaine session 5 in morning.
Self -Administered cocaine session 6 in afternoon.
Conduct clinical assessments (POMS, CGI-I).
Leave CRS unit.

Study Day 12

Arrive at IDAS
Collect urine for pregnancy test and urine drug screen.
Perform and record Breathalyzer and vital signs.
Perform a 12-Lead ECG.
Record brief substance craving scale and AE.
Administer COWS if opioid user.
Update concomitant medication.
Conduct clinical assessments (POMS, CGI-I, Stroop, and XY Go-No Go).
PI (or designee) conduct assessment for lorcaserin side effects.
Leave IDAS

Follow-Up Days (Day 15, 19) Conducted at IDAS

Collect urine for pregnancy test and urine drug screen.
Perform and record Breathalyzer and vital signs.
Perform a 12-Lead ECG and brief physical exam (Day 19 only).
Record brief substance craving scale and timeline follow back cocaine use.
Update concomitant medication.
Conduct clinical assessments (POMS, CGI-I, and C-SSRS).

Table 2. Overview of Study Procedures

Study Day	Day 1	Day 2
Study Visit	One	Two
Procedure Morning Session	Arrive at CRS, Three Screening Doses of Cocaine (NexFin monitoring)	Arrive at CRS 10mg Cocaine for PK
Procedure Afternoon Session	Impulsivity Testing Depart from CRS	Three Doses of Cocaine, Cardiovascular (NexFin monitoring) Cardiac Biomarkers (4-6 hrs from last dose) Subjective Ratings Depart from CRS
Study Drug	Placebo 8:00 a.m.	Placebo 8:00 a.m

Study Day	Day 3	Day 4	Day 5	Day 6	Day 7
Study Visit	Three	Four	Five	Six	Seven Arrive at CRS ECG
Procedure Morning Session	Arrive at CRS Cocaine Self Administration	Arrive at IDAS ECG Impulsivity Testing	Arrive at IDAS ECG	Arrive at CRS ECG 10mg Cocaine for PK, Lorcaserin blood levels	Cocaine Self Administration

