The subject would make a series of choices using the PR schedule between ascending value money options (\$5) or cocaine (0 mg or 25 mg/i.v. infusion) using a patient controlled (PCA pump). Choices for money will be verbally indicated to the investigator. Infusions will be made over a 2 min period followed by a 13 min time-out period. Subjects will receive the cash or cocaine doses (0 or 25 mg) immediately after they meet the progressive ratio criteria for each choice, providing vital signs remain within the preset intervals. If the subject chooses all cocaine options in the cocaine choice session and no money, they will receive a maximum of 120 mg cocaine, i.v. Money choices will be given directly to the patient after choice session, but this can only be spent after departing from the CRS. All infusions on this day will be double-blinded and counterbalanced in their presentation among subjects.

Cardiovascular Monitoring During Cocaine Infusions and Cocaine Self-Administration Procedure

Cardiovascular monitoring by continuous measuring heart rate/ECG and blood pressure starting 15 minutes prior to each of the 4 cocaine infusions and continued for at least 60 minutes following each dose. PI/Co-I or their medically qualified designees will be present during all cocaine infusions to monitor and intervene if necessary. For the sessions of cocaine infusions on Day 1, 2, 6, and 10, non-invasive monitoring of cardiac hemodynamics will be performed with the NexFin finger cuff system (Edwards Life Sciences).

Criteria for withholding Cocaine Administration

Cocaine administration will not be initiated if:

- Clinically significant arrhythmias
- Resting pulse > 130 bpm
- QTc increase of greater than 30ms over baseline
- Blood pressure above 165mm Hg systolic and 100mm Hg diastolic.
- Behavioral manifestations of cocaine toxicity (agitation, psychosis, inability to cooperate with study procedures).

If cardiovascular measures have not returned to acceptable levels (heart rate <130 bpm, diastolic pressure <100mmHg, and systolic pressure <165 mmHg, QTc <30ms over baseline), the next session will be delayed by 15 min, after which these measures will be repeated.

Stopping Criteria for Subject Participation

Subject participation will be terminated if any of the following events occur:

The following values do not return to acceptable limits within appropriate time frames (approximately 30 minutes);

- Systolic BP > 180 mm Hg
- Diastolic BP > 120 mm Hg

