- Heart rate > (220 – age x 0.85) bpm
- QTc > 470ms
- Participants must continue to meet other inclusion criteria in order to remain in the protocol

ADVERSE EXPERIENCE REPORTING AND DOCUMENTATION

Adverse Events

Adverse Events (AEs) will be identified through daily interviews with participants and noted at any visit. The data will be entered on the standard VCU IRB AE and SAE forms. Continuous logs of all SAEs and AEs will be maintained. SAEs will be reported to the VCU IRB, the NIDA PO, the DSMB and the US FDA (when appropriate) as described above. In addition to immediate reports where appropriate, there will be annual reports and descriptions in the results section of publications.

Table 4. AE Severity Grading

Severity (Toxicity Grade)	Description
Mild (1)	Transient or mild discomfort; no limitation in activity; no medical intervention or therapy required. The subject may be aware of the sign or symptom but tolerates it reasonably well.
Moderate (2)	Mild to moderate limitation in activity, no or minimal medical intervention/therapy required.
Severe (3)	Marked limitation in activity, medical intervention/therapy required, hospitalizations possible.
Life-threatening (4)	The subject is at risk of death due to the adverse experience as it occurred. This does not refer to an experience that hypothetically might have caused death if it were more severe.

AE Relationship to Study Drug

The relationship of an AE to the study drug will be assessed using the following the guidelines in 5. Table 5. AE Relationship to Study Drug

Relationship to Drug	Comment
Definitely	Previously known toxicity of agent; or an event that follows a reasonable temporal sequence from administration of the drug; that follows a known or expected response pattern to the suspected drug; that is confirmed by stopping or reducing the dosage of the drug; and that is not explained by any other reasonable hypothesis.
Probably	An event that follows a reasonable temporal sequence from administration of the drug; that follows a known or expected response pattern to the suspected drug; that is confirmed by stopping or reducing the dosage of the drug; and that is unlikely to be explained by the known characteristics of the subject's clinical state or by other interventions.

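### The rule for withholding cocaine requires both blood pressure limits to be exceeded, so an isolated systolic or diastolic rise does not block a day's first infusion

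*Combined protocol and SAP*

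**What the plan says.** Under *Criteria for withholding Cocaine Administration*, the list of conditions that prevent an infusion from starting has a single blood pressure entry: "Blood pressure above 165mm Hg systolic and 100mm Hg diastolic".

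The next paragraph, under the same heading, defines acceptable levels as "heart rate <130 bpm, diastolic pressure <100mmHg, and systolic pressure <165 mmHg, QTc <30ms over baseline". If measures have not come back to those levels, "the next session will be delayed by 15 min, after which these measures will be repeated".

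*Stopping Criteria for Subject Participation* opens with "Subject participation will be terminated if any of the following events occur" and puts systolic above 180 and diastolic above 120 on separate lines, each subject to failure to settle within about 30 minutes. Its last line reads "Participants must continue to meet other inclusion criteria in order to remain in the protocol". *Early Discontinuation of Study Drug* also separates the two pressures (systolic above 180, diastolic above 110), as possible reasons for stopping.

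Table 2 gives the morning procedure on both Day 6 and Day 10 as "10mg Cocaine for PK, Lorcaserin blood levels", ahead of the ascending doses in the afternoon. In the self-administration sessions, a chosen dose is released only if vital signs stay within preset ranges, which that section does not define.

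**The concern.** A rule for accepting a subject can properly join two upper limits with *and*: both pressures must be low enough. A rule for withholding is the negation of that, and its limits must be joined with *or*. The withholding entry keeps the *and*, so it acts only when both pressures are high.

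This is the written pressure check before intravenous cocaine is given. *Risks of Lorcaserin Combined with Cocaine* states: "The combination of lorcaserin and cocaine has not been studied in humans". *Risks of Lorcaserin Administration* adds: "In other populations, lorcaserin has been associated with a modest increase in blood pressure". A raised resting pressure before the first infusion on a lorcaserin day is therefore conceivable. Staff could give cocaine at 170/90 and still be following the withholding list to the letter.

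**Working it through.** The protocol gives no figure to reproduce. The check applies each written rule to the same readings.

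**Rules** (S = systolic, D = diastolic, mm Hg)

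- Withholding list as written: withhold if S > 165 *and* D > 100.
- Following paragraph: acceptable only if S < 165 *and* D < 100; otherwise delay.
- Stopping criteria: S > 180 *or* D > 120.
- Early discontinuation: S > 180 *or* D > 110.
- Corrected rule: withhold if S ≥ 165 *or* D ≥ 100.

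| Reading | List as written | Following paragraph | Stopping or discontinuation limit exceeded | Corrected rule |
|---|---|---|---|---|
| 170/90 | not withheld (90 is not > 100) | delay (170 is not < 165) | no | withheld |
| 150/105 | not withheld (150 is not > 165) | delay (105 is not < 100) | no | withheld |
| 170/105 | withheld | delay | no | withheld |
| 150/90 | not withheld | acceptable | no | not withheld |
| 165/100 | not withheld | delay | no | withheld |

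The list and the paragraph disagree at 170/90, 150/105 and 165/100. The corrected rule is the exact negation of the paragraph's acceptable levels, so the two agree on every row. Changing only *and* to *or* while keeping the strict inequalities would leave the mismatch at exactly 165 or 100.

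**Range of readings missed.** The list does not withhold when S is above 165 with D at or below 100, or when D is above 100 with S at or below 165. Up to S = 180 and D = 120 (D = 110 under early discontinuation), no other numerical limit in these sections is exceeded either. Above those values the other limits come into play, but one depends on failure to settle in about 30 minutes and the other is a list of possible reasons for stopping study drug. Neither is a clear bar before an infusion.

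**Does the following paragraph close the gap?** Its condition is that measures have not returned to acceptable levels, and its consequence is a delay of the next session. Both presuppose something earlier, most naturally an earlier infusion that raised the pressure. It can be read to cover the later 20 and 40 mg steps, although *session* is loosely used. It does not clearly cover the first infusion of a day.

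**Does the continuing-eligibility line close it?** It is unclear whether the line includes the entry limit of 140/90. If it did, the 165/100 rule would be redundant. After screening, Appendix 1 schedules the eligibility re-check only on Days 1 and 2, and lorcaserin starts on the evening of Day 3.

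**Number of infusions**

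- First infusion on Days 6 and 10, Group B: 12 × 2 = 24. All are 10 mg, whether the first infusion is the pharmacokinetic dose (Table 2) or the first step of the dosing session (*Dosage/Dosage Regimen*).
- Conditional: first 25 mg choice on Days 7 and 11, Group B: at most 12 × 2 = 24. This assumes that the undefined preset ranges are these limits and that the subject chooses cocaine. It is an upper bound, because Table 3 counterbalances the order and some 25 mg sessions fall in the afternoon, where the following paragraph has a better claim to apply.

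**The case against.** The strongest reply is that this is a drafting slip whose meaning the same section supplies. The entry criterion uses *and* correctly for pressures below a limit, the withholding entry looks like the same phrase turned round, and the acceptable levels sit directly beneath it. A clinician reading the whole section would not regard 170/90 as acceptable.

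The setting is also protective. Subjects enter below 140/90 without hypertension. Monitoring starts 15 minutes before infusions, an investigator or medically qualified designee attends all of them, and a physician directly supervises administration. On Day 6 the morning capsule is placebo for everyone, and Group B's last lorcaserin dose was the evening before. The infusions clearly affected are at 10 mg, which subjects have already received on Days 1 and 2. No endpoint or analysis depends on the wording.

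Much of this stands. *Or* was very probably intended, harm would require a supervising physician to apply the literal text against the neighbouring paragraph, and the likelihood of a qualifying reading is unknown. What does not follow is that the text can be left alone. The neighbouring paragraph addresses a different moment, and clinical attendance is judgement, which a written threshold is there to bound.

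**Conclusion.** The withholding rule is wrong as written. It lets a day's first cocaine infusion proceed with an isolated systolic pressure above 165 or an isolated diastolic pressure above 100, and it conflicts with the limits set out immediately below it. The clear exposure on lorcaserin is 24 infusions at the lowest dose, plus at most 24 first 25 mg choices under the two assumptions given above. These count opportunities; the number of actual readings in the gap cannot be estimated from the documents.

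The literal reading of *and* is certain. That the following paragraph does not reach a first infusion is the more natural reading, but not the only possible one. The existing safeguards keep the practical risk modest. The correction is still worth making, because this is a safety threshold in an untested combination.

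**What to change.** Replace the blood pressure entry with: systolic 165 mm Hg or higher, or diastolic 100 mm Hg or higher. State that it is checked before every infusion, including the pharmacokinetic dose and the first infusion of each day. In the following paragraph, refer to the next infusion in place of the next session. In the self-administration section, state that these limits are the preset vital-sign ranges governing release of a chosen dose.

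The cost is an amendment to the wording, which under *Protocol Amendments* needs prior written IRB approval, and a matching check on the case report form. The operational downside is perhaps a few more 15-minute delays.

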- 2) Days 3-6: All subjects will be seen on the CRSU on days 3 and 6, and at the IDAS clinic on days 4 and 5. On days 3-6, subject group A will receive one placebo pill twice daily, and group B will receive one placebo pill in the morning and one matching lorcaserin 10 mg pill in the evening, for a total dose of 10 mg daily. ECG with QTc will be performed daily. If the QTc is prolonged greater than 30ms over baseline lorcaserin dosage will be held.
- 3) Day 7: All subjects will receive one placebo pill in the morning in single blind fashion. Following Cocaine Self-administration sessions and impulsivity testing the subjects will leave the unit.
- 4) Days 8-10: All subjects will be seen at the IDAS clinic on Days 8 and 9 and subjects in group B will have a blinded dosage increase to 10 mg of lorcaserin twice daily for Days 8-11 (Days 10 and 11 will take place at the CRSU). Vital signs including heart rate, blood pressure and respiration rate will be obtained before placebo/lorcaserin administration. ECG with QTc will be performed daily under the supervision of a study physician. If the QTc is prolonged greater than 30ms over baseline lorcaserin dosage will be held.
- 5) Day 11: All subjects will be seen on the CRSU and receive placebo/lorcaserin in the morning followed by the last cocaine self-administration session.
- 6) Day 12: Subjects will be seen at IDAS for study procedures.
- 5) Cocaine Infusion Sessions (Days 1, 2, 6, and 10): All subjects will undergo an ascending dose intravenous cocaine administration after admission on day 1 to ensure safety of later cocaine studies.

To assess the safety and subjective effects of cocaine in the presence of lorcaserin, subjects will receive ascending doses of intravenous cocaine (10 mg, 20 mg, 40 mg), with each cocaine administration separated by

one hour. In addition, 0 mg cocaine (saline) infusion will be randomly given after the first dose of cocaine in order to aid in blinding investigators and subjects to the order of drug administration. Infusions will be carried out hourly starting from 1 hour after placebo/lorcaserin for 4 times (on Day 1, 2, 6, and 10). An example dose by session diagram is shown below. Note that the 0 mg dose is randomly given after the first dose of cocaine. Monitoring will be continued for 1 hour after the last dose of cocaine.

Dose	Dose Session 1	Dose Session 2	Dose Session 3	Dose Session 4
1	10 mg Cocaine	10 mg Cocaine	10 mg Cocaine	10 mg Cocaine

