
[contact]

[contact], [name]

DISCONTINUATION AND REPLACEMENT OF SUBJECTS

Early Discontinuation of Study Drug

A subject may be discontinued from study treatment at any time if the subject, the investigator, or the Sponsor feels that it is not in the subject's best interest to continue. The following is a list of possible reasons for study treatment discontinuation:

Subject withdrawal of consent (or assent)

Subject is not compliant with study procedures

Adverse event that in the opinion of the investigator would be in the best interest of the subject to discontinue study treatment

Protocol violation requiring discontinuation of study treatment

Lost to follow-up

Sponsor request for early termination of study

Positive pregnancy test (females)

Chest discomfort or shortness of breath consistent with ischemia

Systolic BP > 180 mmHg

Diastolic BP > 110 mmHg

Heart rate > Maximum predicted heart rate ($> 220 - \text{age} \times 0.85$) bpm.

If a subject is withdrawn from treatment due to an adverse event, the subject will be followed and treated by the Investigator until the abnormal parameter or symptom has resolved or stabilized.

All subjects who discontinue study treatment should come in for an early discontinuation visit as soon as possible and then should be encouraged to complete all remaining scheduled visits and procedures.

All subjects are free to withdraw from participation at any time, for any reason, specified or unspecified, and without prejudice.

Reasonable attempts will be made by the investigator to provide a reason for subject withdrawals. The reason for the subject's withdrawal from the study will be specified in the subject's source documents Refer to Section 10 for early termination procedures.

Withdrawal of Subjects from the Study

A subject may be withdrawn from the study at any time if the subject, the investigator, or the Sponsor feels that it is not in the subject's best interest to continue.

All subjects are free to withdraw from participation at any time, for any reason, specified or unspecified, and without prejudice.

Reasonable attempts will be made by the investigator to provide a reason for subject withdrawals. The reason for the subject's withdrawal from the study will be specified in the subject's source documents.

Replacement of Subjects

Subjects who withdraw from the study treatment will be replaced.

Subjects who withdraw from the study will be replaced.

Protocol Violations

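### The heart-rate stopping limit is mis-bracketed: as printed it exceeds 220 - age at every eligible age and lies 33 bpm above 85% of that figure

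*Combined protocol and SAP*

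**What the plan says.** Stopping Criteria for Subject Participation is a mandatory rule: "Subject participation will be terminated if any of the following events occur". Its numeric limits apply when "The following values do not return to acceptable limits within appropriate time frames (approximately 30 minutes" or so. The heart-rate entry is "Heart rate > (220 – age x 0.85) bpm". The same list adds "Participants must continue to meet other inclusion criteria in order to remain in the protocol".

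Early Discontinuation of Study Drug gives "Heart rate > Maximum predicted heart rate", followed in parentheses by the same expression, again with no bracket around 220 - age. That list is permissive: it names reasons for which study drug may be stopped.

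Neither section gives a worked bpm value, and no section says in words that 85% of maximum is meant. Inclusion Criteria set the age range at 18 to 59. Criteria for withholding Cocaine Administration separately holds a dose when resting pulse is above 130 bpm.

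**The concern.** A factor of 0.85 beside 220 - age suggests a limit of 85% of age-predicted maximum. As bracketed, 0.85 multiplies age alone, which raises the limit above 220 - age instead of lowering it. A person who follows the printed bracket and a person who reads the line as 85% of maximum would apply limits 33 bpm apart to the same subject.

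The protocol states that "The combination of lorcaserin and cocaine has not been studied in humans", and the same section (Risks of Lorcaserin Combined with Cocaine) relies on stopping criteria for excessive cardiovascular responses as a safeguard. Heart rate is one of four numeric triggers in the mandatory list, with systolic pressure, diastolic pressure and QTc.

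The withholding rule matters least after the last infusion of a day. The dosage section says "Monitoring will be continued for 1 hour after the last dose of cocaine", but no further dose remains that day for the rule to hold back. From then on, the numeric stop bears on whether the subject goes on to the next cocaine day.

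**Working it through.** **Inputs.** The printed expression comes from Stopping Criteria for Subject Participation and is repeated in Early Discontinuation of Study Drug. Ages 18 to 59 come from Inclusion Criteria, and 130 bpm from the withholding criteria. The plan gives no bpm value, so there is no stated figure to reproduce. Taking 220 - age as the maximum predicted heart rate is an assumption, based on the label in the second section.

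**Formulas.**
- Printed limit: P = 220 - 0.85 x age
- Predicted maximum: M = 220 - age
- 85% of maximum: R = 0.85 x (220 - age) = 187 - 0.85 x age
- P - M = 0.15 x age, which is positive at every age
- P - R = 220 - 187 = 33 bpm at every age

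| Age | P | M | R | P - M | P / M | P - R | R - 130 |
|---|---|---|---|---|---|---|---|
| 18 | 204.7 | 202 | 171.7 | 2.7 | 101.3% | 33 | 41.7 |
| 25 | 198.75 | 195 | 165.75 | 3.75 | 101.9% | 33 | 35.75 |
| 40 | 186.0 | 180 | 153.0 | 6.0 | 103.3% | 33 | 23.0 |
| 50 | 177.5 | 170 | 144.5 | 7.5 | 104.4% | 33 | 14.5 |
| 59 | 169.85 | 161 | 136.85 | 8.85 | 105.5% | 33 | 6.85 |

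The two inequalities were checked at all 42 integer ages from 18 to 59, and both hold throughout.

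**The 30-minute clause.** It can mean that the rate stays above the limit, or that it exceeds the limit and then fails to fall to an acceptable level, for example below 130 bpm. On either reading the limit must first be exceeded. A 40-year-old whose rate peaks between 153 and 186 bpm and does not recover in about 30 minutes therefore misses the heart-rate stop as printed. Under the 85% limit that subject could be stopped: on the first reading if the rate stays above 153 bpm, on the second if it simply fails to recover.

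**Exposure.** The plan has "Cocaine Infusion Sessions (Days 1, 2, 6, and 10" and, in addition, self-administration on Days 3, 7 and 11, which makes seven cocaine days. Six of them (Days 1, 2, 3, 6, 7 and 10) have a later cocaine day. With all 18 subjects completing and taking an infusion each day, that gives 6 x 18 = 108 subject-days on which a stop could end later cocaine exposure, as an upper bound. Lorcaserin starts on the evening of Day 3 and only in the 12 Group B subjects. The days with lorcaserin on board and a later cocaine day are therefore 6, 7 and 10, or 3 x 12 = 36 of the 108.

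**The case against.** The strongest objection concerns intent. The only words the plan attaches to the formula, maximum predicted heart rate, favour 100%, and on that reading the error is 2.7 to 8.85 bpm, not 33. This stands as a limit on the claim: the 33 bpm gap is conditional. The shared slope of P and R is consistent with a misplaced bracket but does not prove what was meant. Under a 100% intention, however, the 0.85 has no purpose and the printed limit still exceeds the maximum it is named after.

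The second objection is practical. Staff may key the expression left to right and obtain 85% of maximum anyway. The trial has one centre, and a medically qualified person attends every infusion. Tachycardia is listed as a sign of cocaine toxicity with treatment protocols in place, and a screening infusion precedes randomization. The continued-inclusion item, if it covers the resting pulse below 95 bpm required at entry, is far stricter than either formula. All of this makes it unlikely that a sustained high rate would go unmanaged. But a pulse that settles overnight would pass the entry limit the next day, the withholding rule delays a dose without ending participation, and a numeric stop exists so that termination does not rest on discretion alone.

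Third, 108 subject-days is wider than the lorcaserin-cocaine combination itself, for which 36 is the relevant count. Neither figure measures harm. The plan gives no heart-rate distribution, so no trigger frequency can be stated.

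**Conclusion.** The concern holds. The printed limit is wrong on either plausible intention, provided 220 - age is the predicted maximum. The size of the error depends on which limit was meant, and the plan does not settle that; 85% is the likelier reading. The effect is to weaken one automatic termination trigger among several safeguards. It should be fixed, although it does not undermine the safety plan as a whole.

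**What to change.** The study's medical lead confirms the intended limit.

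- If 85% of maximum is meant, print 0.85 x (220 - age) bpm in both Stopping Criteria for Subject Participation and Early Discontinuation of Study Drug. Add example values (171.7 at age 18, 153.0 at 40, 136.85 at 59) and relabel the second entry as 85% of maximum predicted heart rate.
- If 100% is meant, print 220 - age in both places and delete the 0.85.

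A minor wording point can go into the same amendment. The blood-pressure line of the withholding rule joins the systolic and diastolic limits with 'and', while the sentence on return to acceptable levels requires each to be under its limit. Changing 'and' to 'or' makes them agree. The gap is mainly at the first dose of a session, because the later sentence covers subsequent doses.

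The cost is a wording amendment, with no new procedure and no change to the planned analyses. Under the 85% limit a few more subjects might be stopped and then replaced, as Replacement of Subjects provides. These would mainly be older subjects: at age 59 that limit is only 6.85 bpm above the withholding threshold.
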